Therefore, it is important to identify fragile patients to implement prevention programs through global geriatric assessments (CGA Comprehensive Geriatric Assessment). Just by having more clinical attention for more fragile patients after major surgery there can be better results of short and long-term postoperative mortality (22). Likewise, as demonstrated in randomized clinical studies, prehabilitation and global geriatric assessment programs improve the results in terms of postoperative complications and hospital stay (30, 31, 32).

The CGA is an established method to evaluate and optimize the physical state, the psychological, functional and social problems in elderly patients in order to improve the results of the treatments. It implies an interdisciplinary evaluation of multiple domains, followed by planning for analysis, treatment, rehabilitation and long-term follow-up (33).

This allows, in the first place, to intervene before an operation, to increase the physiological reserve of a patient, especially with exercise and nutrition (34, 35). In addition, the therapeutic decision can be guided by adapting the surgical recommendations to the physiological capacity of the patient; second, the knowledge of the increased risk of complications and the possible need for transfer to institutions (especially in patients who live alone) prepares patients and their families for postoperative evolution (8).

The majority of studies published in the literature on the relationship between frailty and postoperative results are retrospective studies, which evaluate populations of patients undergoing major surgery and who, in general, analyze short-term results (30-day mortality) (12, 20, 22, 24, 25, 26, 27, 28, 29). None of these takes into account the impact of surgery on the quality of life of this group of patients. Among all these studies there is very little information about the influence of frailty in gastric cancer surgery. There is only one retrospective study that focuses only on gastric cancer surgery, using the Groningen index and revealing an increase in in-hospital mortality and serious complications (Clavien-Dindo complications score ≥ 3) in fragile patients (25). Objective

The aim of the present study is to assess the impact of frailty on the results of gastric cancer surgery (long-term postoperative morbidity and mortality, hospital stay, readmissions, need of transfer to institution of medium or long stay and quality of life).

Methods

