Study design: Patients and participating Centers This is a prospective and multicenter cohort study, within the Spanish EURECCA Esophagogastric Cancer Project, to investigate the impact of frailty on the postoperative results of surgery for gastric cancer in elderly patients. Inclusion/exclusion criteria will be following:

- Inclusion criteria: Patients ≥ 70 years diagnosed with gastric cancer (whether or not they have received neoadjuvant treatment) and candidates for elective surgical resection with potentially curative intention (R0) even if it is finally an R1 or R2.
- Exclusion criteria: Patients with disseminated gastric cancer or candidates for palliative surgery, as well as those patients who do not give their consent to participate. Participation in the study will be offered to all centers that are currently part of the Spanish EURECCA Esophagogastric Cancer Registry. Those hospitals that show their desire to participate must sign the Letter of Commitment.

The Spanish EURECCA Upper GI Cancer Group was created in 2012 and collects prospective and validated information about all the patients submitted to surgery for esophagogastric cancer in the public hospitals of four Spanish Autonomous Communities, with the aim of having reliable information on the results of this surgery and constitute a platform for the development of research projects.

Data collection

A specific on-line database will be created for this project, with all the security measures (user and password for individual access), in which the researchers will record the data referring to the Frailty and Quality of life questionnaires. On this basis, the researcher will use the patient identifier (random 6-digit code) previously established by the on-line registration of the EURECCA Project where the patients variables are usually collected.

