The characteristics of fragile and non-fragile patient groups will be compared through frequency tables. The Chi-square test will be used to compare the differences between the categorical variables and the ANOVA test for the continuous variables. Different analyzes are proposed according to the study variables that are to be analyzed. For dichotomous type response variables (90- day mortality, 12-month mortality, incidence of serious complications, incidence of in-hospital death in patients with complications, and hospital readmission at 30 days after discharge), a multivariate logistic regression will be used to evaluate the risk (odds ratio) of these variables. For continuous response variables (ICC score) at 30 days after the intervention, and number of days of hospital stay), linear regression models will be used. For the variable categorical response of the patient after hospital discharge, an ordinal logistic regression model will be done. All regression models will be adjusted for age, sex, body mass index (BMI), type of gastrectomy, center volume, neoadjuvant treatment and degree of frailty. Regarding HRQoL analysis, the mean scores and 95% confidence intervals for the different domains of preoperative HRQoL and one year after surgery will be calculated. Changes of more than 10 points on a scale from 0 to 100 will be considered clinically relevant as previously suggested in other publications (40). Work plan The study period includes: Patient recruitment. Follow-up for 1 year to meet the objectives of the study.

The study starts by assessing the fragility of the patients. Once the stage study is completed, the potential curative surgery is determined and after the case presentation in the Multidisciplinary Tumor Committee of each institution, the G8 questionnaires and modified fragility index will be carried out to identify the state and degree of fragility, 2 weeks prior to surgery. The result of the evaluation of the frailty of the patient, will be performed after the Multidisciplinary Committee, thus it will not modify the therapeutic decision.

To measure the Health Related Quality of Life (HRQoL), the QLQ-C30 and QLQ-STO22 questionnaires, will be delivered at the time of the preoperative visit and 12 months after surgery.

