Patients will be asked to fill them in their home. If any patient reports difficulty in understanding the questionnaires, additional help will be provided. Once the questionnaires are received, it will be verified that all the questions have been answered. Otherwise, patients will be contacted in order to complete the questionnaire via telephone. If it is not possible to complete the answers of more than half of the questions on a scale, they will be excluded from the statistical analysis, according to the recommendations of the EORTC (39). All responses from the EORTC QLQ-C30 and STO22 questionnaires will be transformed linearly into scores ranging from 0 to 100 to standardize the score. In functional scales, high scores represent better quality of life (better function) while high scores in symptom scales and items involve more symptoms.

In addition, the variables described in the methodology section will be collected and analyzed:

- Incidence of serious complications (Clavien-Dindo complications score ≥ 3)
- Complication Comprehensive Index (CCI) score during the hospital stay and at 30 days after the intervention
- Incidence of in-hospital death in patients suffering from a complication (failure-to-rescue)
- Hospital stay
- Destination of the patient after hospital discharge
- Hospital readmission within the first 30 days after the discharge
- Mortality at 90 days after the intervention
- Mortality at 12 months after the intervention

In addition to the previously described questionnaires and the main and secondary variables, data related to the prevalence of comorbidities of the patients (Charlson Comorbidity Index, ASA), the stage

study, preoperative optimization, surgical intervention, histopathology and follow-up will be collected. All these data are already systematically collected in the EURECCA Register. Ethical considerations This project is included in the EURECCA Registry, which was presented and approved by the Parc de Salut MAR Clinical Research Ethical Committee (CEIC PSMar) in 2013 in its initial version (nº 2013/5047/I). The amendment of the version, dated 9th June 2016, was approved by the CEIC PSMar and by the respective Clinical Research Ethical Committees of the participating centers. The EURECCA Registry also has a specific Patient Information Sheet and Informed Consent, approved in the 1.2 version of March 2018.

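### The 12-month mortality model leaves out tumour stage, which is established before frailty is scored, so the frailty odds ratio may be confounded in either direction

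*Combined protocol and SAP*

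**What the plan says.** The Statistical analysis plan section assigns logistic regression to the dichotomous outcomes, 12-month mortality among them, and then gives one list for all models: "All regression models will be adjusted for age, sex, body mass index (BMI), type of gastrectomy, center volume, neoadjuvant treatment and degree of frailty". Neither clinical nor pathological stage appears. No other section adds stage to a model, explains its absence, or plans a sensitivity analysis with it.

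Other places bear on whether stage could be used and whether it matters:

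- **Timing.** The Work plan says "Once the stage study is completed, the potential curative surgery is determined". The frailty questionnaires follow the tumour committee, two weeks before surgery.
- **Availability.** The variables to be collected include "data related to the prevalence of comorbidities of the patients (Charlson Comorbidity Index, ASA), the stage" and, continuing the same list, "study, preoperative optimization, surgical intervention, histopathology and follow-up will be collected". The text adds: "All these data are already systematically collected in the EURECCA Register".
- **Range of stage.** The Study design section reads "Exclusion criteria: Patients with disseminated gastric cancer or candidates for palliative surgery", and also excludes those who do not consent. Nothing restricts stage among potentially curable cases.
- **Description of groups.** "The characteristics of fragile and non-fragile patient groups will be compared through frequency tables". Stage is not named for these tables.
- **Aim.** The Objective is to assess the "impact of frailty on the results of gastric cancer surgery (long-term postoperative morbidity and mortality", among other results. Twelve-month mortality is a listed secondary outcome.

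**The concern.** This is a non-randomised cohort, and regression adjustment is the only means the plan names for separating frailty from other differences between the groups. Stage is an obvious candidate confounder for death within a year of cancer surgery. It is established before frailty is scored, so adjusting for clinical stage does not mean adjusting for a consequence of the operation.

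The bias could go either way. If advanced tumours impair function, frail patients would tend to have later stage and the odds ratio would be too high. Functional status is, however, only one of the five domains named for the modified frailty index. If frail patients reach curative surgery mainly when their disease is less advanced, the odds ratio would be too low.

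Neoadjuvant treatment and type of gastrectomy are on the list and stand in for stage only in part. The descriptive tables may reveal an imbalance but cannot remove it, and adding stage after seeing one would be a data-driven choice.

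**Working it through.** The plan gives no 12-month mortality, stage distribution or stage effect, so it has no figure of its own to reproduce here. The calculation below shows what size of shift is plausible.

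**From the plan (Sample size section).** 276 non-frail and 92 frail patients, 368 in total. 90-day mortality is 0.6% and 4.3%.

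**Assumed.** No true frailty effect. Stage has two levels, with advanced stage in 40% of the non-frail and in 20%, 30%, 50% or 60% of the frail. Three pairs of 12-month mortality (early, advanced) are used: 8% and 14.8%; 8% and 28%; 5% and 25%. The stage odds ratios are then 2.0, 4.5 and 6.3. No other covariate is adjusted for.

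**Step 1: risk in each group.** Risk = (1 − share advanced) × early risk + share advanced × advanced risk. For 8% and 28%:
- non-frail: 0.6 × 8% + 0.4 × 28% = 16%
- frail with 60% advanced: 0.4 × 8% + 0.6 × 28% = 20%

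**Step 2: frailty odds ratio without stage.** (0.20/0.80) / (0.16/0.84) = 0.2500/0.1905 = 1.31, where the true value is 1.

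**Step 3: compare with precision.** SE of the log odds ratio = √[1/(276 × 0.16) + 1/(276 × 0.84) + 1/(92 × 0.20) + 1/(92 × 0.80)] = 0.308. The shift is ln(1.31)/0.308 = 0.88 SE.

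**All scenarios.** Each cell gives the odds ratio, with the shift in SE in parentheses.

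| Early / advanced risk (stage OR) | Non-frail risk | Frail 20% advanced | 30% | 50% | 60% |
|---|---|---|---|---|---|
| 8% / 14.8% (2.0) | 10.7% | 0.86 (0.37) | 0.93 (0.18) | 1.07 (0.18) | 1.14 (0.36) |
| 8% / 28% (4.5) | 16% | 0.72 (0.93) | 0.85 (0.46) | 1.15 (0.45) | 1.31 (0.88) |
| 5% / 25% (6.3) | 13% | 0.66 (1.02) | 0.83 (0.50) | 1.18 (0.49) | 1.37 (0.95) |

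A second set of assumptions (stage odds ratio 2 to 5, shares of 40% to 60%, 5% to 10% risk in early-stage non-frail patients) gives a similar range, 0.75 to 1.34.

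**Step 4: what is not confounding.** With 40% advanced in both groups and a true stage-adjusted frailty odds ratio of 2, the odds ratio without stage is 1.98, 1.88 and 1.86 for the three risk pairs. That gap is non-collapsibility of the odds ratio.

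**Step 5: room in the model.** At an assumed 12-month mortality of 10% to 25% there are 368 × 0.10 = 37 to 368 × 0.25 = 92 deaths.

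| Terms | Deaths per term |
|---|---|
| 7 (planned list, one term each) | 5.3 to 13.1 |
| 8 (one stage term) | 4.6 to 11.5 |
| 9 (two stage terms) | 4.1 to 10.2 |
| 10 (one stage term, four-level frailty index as three terms) | 3.7 to 9.2 |

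At 90 days the plan's own rates give 276 × 0.006 + 92 × 0.043 = 1.66 + 3.96 = 5.6 deaths, or 5.6/7 = 0.8 per term.

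**The case against.** The strongest reply is that no bias has been demonstrated. Omitting stage confounds the estimate only if stage still differs by frailty once the listed covariates are in the model, and every input above except the group sizes is assumed. That stands, and it is why the point is stated as a possibility. It does not justify the omission, because a plan has to deal with plausible confounders before the data are seen.

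The mechanisms can also be questioned. Frailty is scored after the committee so that it does not alter the treatment decision, which weakens the argument that frail patients are selected for earlier disease. Informal clinical judgement of fitness could still select them, so the argument is weakened but not removed.

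The shifts are modest. A 10-point imbalance moves the estimate by 0.18 to 0.50 SE. Shifts of about 0.9 to 1.0 SE need a 20-point imbalance together with a stage odds ratio of 4.5 or more, and the planned covariates may absorb some of that. This is fair for one secondary outcome. But a bias, unlike random error, does not shrink with more patients.

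Finally, the model is sparse. The scenarios above imply 38 to 63 deaths (276 × non-frail risk + 92 × frail risk), or 4.8 to 7.8 per term with one stage term, which is the lower part of the range in Step 5. That argues for one stage term and for penalisation if deaths are few. An estimate without stage is also informative for identifying patients for prevention programmes, and it would still be reported.

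**Conclusion.** The concern holds. Stage is absent from the only covariate list, that list governs the 12-month mortality model, and the plan itself says the stage study precedes frailty scoring and its data are already in the registry. The size and sign of any bias cannot be fixed from the documents. Under the stated assumptions, a true odds ratio of 1 would read anywhere from 0.66 to 1.37, and closer to 1 if neoadjuvant treatment and type of gastrectomy capture part of stage. The change should be made, because long-term mortality is part of the stated aim and the cost is small. Confidence is medium, since the stage-by-frailty association is unknown. The point is limited to 12-month mortality.

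**What to change.** In the Statistical analysis plan section, for the 12-month mortality model:

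- Add one pre-specified clinical-stage term (two at most), taken from the pre-operative stage study. For patients given neoadjuvant treatment, use staging from before that treatment where the registry holds it.
- State how missing clinical stage is handled.
- Make the stage-adjusted odds ratio the main 12-month result and report the model without stage as a sensitivity analysis. Note there that part of any difference may be non-collapsibility.
- Use pathological stage only in a further sensitivity analysis, because it is measured after frailty and after any neoadjuvant treatment.
- Use penalised logistic regression if deaths are few.

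Leave the 90-day model as it is. The reason is that about 5.6 expected deaths cannot support another term, not that stage could not matter there.

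The cost is SAP wording and a check of the registry's stage variable (coding, timing relative to neoadjuvant treatment, completeness), which the plan does not describe. New data collection is probably not needed. The statistical price of one stage term is a fall from 5.3–13.1 to 4.6–11.5 deaths per term at the assumed mortality.

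### The regression models do not say how correlation between patients of the same hospital is handled: the frailty standard error may be somewhat too small, and hospital differences other than volume could confound the frailty effect

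*Combined protocol and SAP*

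**What the plan says.** The section on study design and participating centres states: "This is a prospective and multicenter cohort study, within the Spanish EURECCA Esophagogastric Cancer Project". It adds: "Participation in the study will be offered to all centers that are currently part of the Spanish EURECCA Esophagogastric Cancer Registry". It gives neither the number of hospitals nor the expected number of patients in each.

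The Statistical analysis plan names three kinds of model:
- For the dichotomous outcomes, including 90-day mortality: "a multivariate logistic regression will be used to evaluate the risk (odds ratio) of these variables".
- For the complication index and hospital stay: "linear regression models will be used".
- For discharge destination: "an ordinal logistic regression model will be done".

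The covariates are the same throughout: "All regression models will be adjusted for age, sex, body mass index (BMI), type of gastrectomy, center volume, neoadjuvant treatment and degree of frailty". Centre volume is the only one measured at hospital level. The documents mention no hospital effect, random intercept, generalised estimating equations, clustered variance or stratification by hospital. The Sample size section compares two proportions and applies no design effect.

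Frailty is a patient-level measurement. Under Work plan: "the G8 questionnaires and modified fragility index will be carried out to identify the state and degree of fragility, 2 weeks prior to surgery".

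**The concern.** Patients treated in the same hospital share surgeons, perioperative routines and discharge arrangements. Two problems can follow when a model ignores this.

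The first is precision. A covariate that is constant within a hospital, such as volume, has only as many independent values as there are hospitals, so an ordinary model overstates how well its coefficient is known. A patient-level covariate such as frailty is affected less, and only if its prevalence also differs between hospitals.

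The second is confounding. Two hospitals of equal volume may differ in stay, readmission and use of institutions after discharge. The Introduction says that prehabilitation and geriatric assessment programmes improve complications and stay. Preoperative optimisation is among the data collected, but it is not in the adjustment set. If hospitals with more frail patients also have longer usual stays, the planned model attributes part of the hospital difference to frailty. This matters more than the first problem, because it concerns the estimate the study exists to produce.

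**Working it through.** **Inputs from the documents.** 276 non-frail and 92 frail patients, 368 in total; 90-day mortality 0.6% and 4.3%; 80% power; one-sided analysis, with the significance level read as 0.05 (all from Sample size).

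**Assumed inputs.** m = 18 patients per hospital (about 20 hospitals); outcome intraclass correlation (ICC) 0.02 to 0.10; frailty ICC 0 to 0.20. The documents give none of these.

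**The plan's own figure.** With a 3:1 ratio and pooled variance, the mean proportion is (0.043 + 3 × 0.006)/4 = 0.01525. The number of frail patients is (1.645 + 0.842)² × 0.01525 × 0.98475 × (4/3) / 0.037² ≈ 90.4, with 271 non-frail. This is close to the stated 92 and 276. Other standard formulas give larger numbers, which is a separate matter. All of them, like the plan's, treat patients as independent.

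**Standard errors.** Design effect = 1 + (m − 1) × ICC(outcome) × ICC(covariate). Understatement of the standard error = 1 − 1/√(design effect). The actual type I error of a nominal two-sided 5% test is 2 × [1 − Φ(1.96/√(design effect))].

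| Covariate | ICC outcome | ICC covariate | Design effect | SE too small by | Type I error |
|---|---|---|---|---|---|
| Frailty, equal prevalence | any | 0 | 1.00 | 0% | 5% |
| Frailty | 0.02 | 0.05 | 1.017 | 0.8% | 5.2% |
| Frailty | 0.05 | 0.10 | 1.085 | 4% | 6% |
| Frailty | 0.10 | 0.10 | 1.17 | 8% | 7% |
| Frailty | 0.10 | 0.20 | 1.34 | 14% | 9% |
| Centre volume | 0.05 | 1 | 1.85 | 26% | 15% |
| Centre volume | 0.10 | 1 | 2.70 | 39% | 23% |

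**Confounding.** A linear-model simulation used 368 patients in 20 hospitals.
- When hospital frailty prevalence was unrelated to hospital outcome, the frailty coefficient was unbiased.
- With an assumed correlation of 0.5 between the two and outcome ICC 0.05 to 0.10, the bias was 0.04 to 0.10 outcome standard deviations, against a standard error of about 0.13.
- Within-hospital estimation removed the bias.

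**What a random intercept does about confounding.** In a linear model the between-hospital information keeps a weight of (1 − ICC)/(1 − ICC + m × ICC) relative to ordinary regression. At ICC 0.05 this is 0.95/(0.95 + 0.90) = 51%; at ICC 0.10 it is 0.90/(0.90 + 1.80) = 33%. A random intercept therefore reduces this confounding but does not remove it. Clustered standard errors leave the estimate unchanged and remove none.

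**Primary outcome.** Expected deaths are 276 × 0.006 + 92 × 0.043 = 1.66 + 3.96 = 5.6. That is too few for hospital terms, and too few for the seven listed covariates.

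**The case against.** The strongest reply is that frailty is the exposure of interest and is measured on each patient, so its standard error is nearly right unless frailty also clusters by hospital. The large figures belong to centre volume, on which the study draws no conclusion, and a wrong standard error for an adjustment term does not alter the frailty interval. The upper end for frailty is also generous. A frailty ICC of 0.20 at the plan's 23% prevalence implies a between-hospital standard deviation of √(0.20 × 0.23 × 0.77) ≈ 19 percentage points, which would be wide when every hospital uses the same two instruments. Finally, sparse deaths trouble the primary model more than clustering does.

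All of this stands, and it limits the size of the point. It does not remove it: no method for within-hospital correlation is named, and volume cannot represent every difference between hospitals.

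A reader might go further and infer that intervals are too narrow in every planned model, or that confounding by hospital is certain. The documents support neither. The first needs both frailty and outcome to cluster; the second needs hospital frailty to move with hospital outcome, and no data are given on either. A reader might also infer that each hospital's own staff score frailty, making scoring drift likely. The documents do not say who administers the instruments, only that researchers record the data.

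**Conclusion.** The omission is real and worth correcting, mainly for the secondary outcomes. If outcomes cluster by hospital, the standard error for centre volume will be too small. The standard error for frailty may be, by about 0% to 14% (type I error 5% to 9%), under an assumed 18 patients per hospital, outcome ICC up to 0.10 and frailty ICC up to 0.20. Hospital differences other than volume could confound the frailty effect on stay, complications, readmission and discharge destination. This is possible, not established. The number of hospitals and both ICCs are assumptions, so these are ranges and not corrections to any stated figure.

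**What to change.** In the Statistical analysis plan:

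1. Add a hospital random intercept to the models for hospital stay, complication index, serious complications, 30-day readmission, discharge destination and 12-month mortality.
2. If such a model does not converge, use hospital-clustered standard errors with a small-sample correction.
3. Add a within-hospital sensitivity analysis for stay, complication index and the other frequent outcomes, using either hospital fixed effects or the hospital mean of frailty as an extra term. Steps 1 and 2 alone do not remove confounding by hospital.
4. For 90-day mortality and failure-to-rescue, keep the simplest model and state that clustering is not modelled.

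The cost is a few sentences in the plan, standard software options and slightly wider intervals. No extra data or patients are needed. Settling this before results are seen also avoids a post hoc choice of model.

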Primary and secondary variables The impact of the frailty on different outcome variables will be evaluated. The main outcome variable will be 90-day mortality after the intervention. Other secondary outcome variables will also be evaluated: incidence of serious complications (Clavien-Dindo complications score ≥ 3), Complication Comprehensive Index (CCI) score (37, 38), hospital stay, incidence of death in patients suffering from a complication (failure to-rescue), hospital readmission within the first 30 days after the discharge, destination of the patient after discharge from hospital [home, social health centers, or geriatric residence], mortality at 12 months after the intervention, quality of life before the intervention and at 12 months.

Frailty evaluation For the assessment of frailty (frailty screening), two questionnaires will be used:

- Questionnaire G8: This is a questionnaire with 8 questions, easy to use, with a total score that varies from 0 to 17 points. Previous studies suggest the score ≤ 14 as a cut-off point to identify the fragile patient, with a sensitivity of 92% and specificity of 52% (36).
- Modified frailty index: This index was described by Velanovich et al. (14), based on a previously validated simplification of the frailty index CSHAFI (Canadian Study of Health and Aging Frailty Index), which was specifically designed to analyze data included in the National Surgical Quality Improvement Program of the American College of Surgeons (ACSNSQIP). It consists of 11 questions with 1 point assigned to each of them on the functional, endocrine, respiratory, cardiovascular and neurological status of the patient. It allows to divide the patients into 4 groups: without frailty (FI = 0), slightly fragile (FI = 1), moderately fragile (FI = 2) and severely fragile (FI ≥ 3).

Postoperative complications Postoperative complications will be classified according to the recommendations proposed by the European Chapter of the International Gastric Cancer Association (EGCA) (unpublished data), its severity through the classification of Clavien-Dindo and the CCI (37, 38). In particular, the CCI will be calculated using the free application that can be found on the website: www.assessurgery.com/calculator_single/.

[Health-related quality of life](#)

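### Quality of life is the only one of nine listed outcomes with no stated model or contrast by frailty, so the plan as written gives no adjusted frailty effect on it

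*Combined protocol and SAP*

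**What the plan says.** All references are to the combined protocol and SAP.

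- **Objective.** The impact of frailty is to be assessed on a list of results: "long-term postoperative morbidity and mortality, hospital stay, readmissions, need of transfer to institution of medium or long stay and quality of life".
- **Primary and secondary variables.** The section opens with "The impact of the frailty on different outcome variables will be evaluated" and its list of secondary outcomes ends with "mortality at 12 months after the intervention, quality of life before the intervention and at 12 months".
- **Statistical analysis plan, modelled outcomes.** Five dichotomous outcomes get logistic regression. Then: "For continuous response variables (ICC score) at 30 days after the intervention, and number of days of hospital stay), linear regression models will be used". Discharge destination gets an ordinal logistic model. The covariate rule is "All regression models will be adjusted for age, sex, body mass index (BMI), type of gastrectomy, center volume, neoadjuvant treatment and degree of frailty".
- **Statistical analysis plan, quality of life.** The analysis is that "the mean scores and 95% confidence intervals for the different domains of preoperative HRQoL and one year after surgery will be calculated". The only rule for interpreting it is "Changes of more than 10 points on a scale from 0 to 100 will be considered clinically relevant".
- **Work plan.** QLQ-C30 and QLQ-STO22 are given at the preoperative visit and at 12 months. Patients are telephoned to complete unanswered items, and a scale with too many unanswered items is dropped. Nothing is said about a 12-month form that is never returned.

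**The concern.** The stated question is what frailty does to quality of life. The stated analysis describes quality of life before and after surgery. It names no frailty group, between-group difference, model or covariate.

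Frail and non-frail patients may well differ in age, BMI, type of operation and preoperative score. The other outcomes get a frailty coefficient adjusted for the listed covariates; quality of life does not. A reader would be left with a crude comparison, if any, for an outcome that is part of the aim and for which patients complete two questionnaires twice. With no contrast fixed in advance, the choice among several defensible ones, across many scales, would be made after the data are seen.

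A second issue follows from the same sentence. Patients who die before 12 months cannot return the second form. Unless both means are restricted to patients with both forms, they may describe different patients, and their difference would then mix change with who survived and replied.

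**Working it through.** The plan states no figure for quality of life that could be reproduced, so the main check is a match of outcomes to analyses.

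**1. Count.**

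| Outcome (Primary and secondary variables) | Analysis (Statistical analysis plan) |
|---|---|
| 90-day mortality (primary) | logistic |
| Serious complications | logistic |
| Death after a complication | logistic |
| 30-day readmission | logistic |
| 12-month mortality | logistic |
| Complication index | linear |
| Hospital stay | linear |
| Discharge destination | ordinal logistic |
| Quality of life | means with 95% CIs at two times |

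Listed: 1 primary + 8 secondary = 9. Modelled with degree of frailty: 5 + 2 + 1 = 8. Left over: 9 − 8 = 1.

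**2. What the planned means can yield.**

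- Means over all patients: a before-after description, with no frailty contrast.
- Means by frailty group at 12 months: a crude difference. With reported CI half-widths h₁ and h₂ for two independent groups, the difference has half-width √(h₁² + h₂²) in large samples.
- Means by frailty group at both times: the within-patient change has variance s₀² + s₁² − 2r·s₀·s₁, where s₀ and s₁ are the SDs of the preoperative and 12-month scores and r is their correlation. Its CI cannot be recovered from separate means without r, and the formula applies only if the same patients contribute at both times.
- A covariate-adjusted difference: not recoverable from any of these means.

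**3. Whether other sentences fill the gap.** The opening chi-square and ANOVA comparison concerns the characteristics of the two groups. At most it reaches preoperative scores, unadjusted. The covariate rule applies to regression models, and none is named for quality of life. The linear regression sentence lists its outcomes, and quality of life is not among them.

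**4. Why the contrast must be chosen.** Let d be the preoperative frail versus non-frail gap, D the 12-month gap, and b the slope of the 12-month score on the preoperative score.

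- Difference in mean change: D − d.
- Difference adjusted for preoperative score: D − b·d.
- They differ in size by (1 − b)·d.

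The documents give neither d nor b. Assuming d of 5 to 10 points and b of 0.3 to 0.6:

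| | b = 0.3 | b = 0.6 |
|---|---|---|
| d = 5 | 3.5 | 2.0 |
| d = 10 | 7.0 | 4.0 |

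**5. Precision, for illustration only.** The unadjusted half-width is 1.96 × SD × √(1/n₁ + 1/n₂). With an assumed SD of 20 to 30 and all of the planned 92 frail and 276 non-frail patients returning both forms, it is 4.7 to 7.1 points. Now assume losses of 35% and 15%, then non-return by 30% and 20% of the rest: 92 × 0.65 × 0.70 ≈ 42 and 276 × 0.85 × 0.80 ≈ 188, giving 6.7 to 10.0. Adjusting for preoperative score at an assumed correlation of 0.5 multiplies these by √(1 − 0.25) = 0.866, giving 4.1 to 6.1 and 5.8 to 8.7. Correlation of frailty with other covariates could widen them. These figures describe the proposed analysis, not the harm done by its absence.

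**The case against.** The best reply is that the plan is being read strictly for quality of life and generously elsewhere. The count of eight reads ICC as the complication index, passes over the in-hospital value of that index (listed in the Work plan without its own model), and accepts frailty as the last item in a covariate list rather than a named exposure. Quality of life sits under a heading that promises to evaluate frailty, and the SAP opens with frail and non-frail groups. Means by group are a natural reading. Much of this stands. A reader might infer that the plan can produce no frailty comparison of quality of life, or none with a confidence interval. The documents do not support that: group means with CIs would give a crude 12-month difference and its interval. What they cannot give is adjustment. For the other eight outcomes an adjusted frailty coefficient does follow from the stated models.

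A second reply is that before-after means serve a need the Introduction names when it says of earlier studies: "None of these takes into account the impact of surgery on the quality of life of this group of patients". That is fair, and the means are worth keeping. They answer what surgery does to quality of life; the Objective asks what frailty does.

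A third is that the outcome is secondary. So are seven of the eight modelled ones.

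Two further limits stand. The absence of a named analysis set, and the open choice between the G8 and the modified frailty index, affect every outcome and are not faults peculiar to this one. It is also tempting to declare the baseline-adjusted 12-month difference the only proper contrast. The documents do not support that. Their relevance rule concerns changes, and the modified frailty index covers functional status while QLQ-C30 has a physical function scale, so adjusting for preoperative score may remove part of the frailty difference.

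**Conclusion.** The point holds in this form: one of nine listed outcomes has no stated model or contrast by frailty, and followed as written the plan gives no adjusted frailty effect on quality of life although the Objective asks for one. This is more than missing detail, because the stated analysis does not answer the stated question. It should be corrected. It does not touch the primary mortality analysis or data collection.

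The conclusion rests on the text and the count alone. It depends on none of the assumed SDs, losses, correlation, gap or slope. A reader might take the half-widths as showing that the study is too imprecise for quality of life; with no SD or attrition in the documents, they cannot show that. Nor can the size or direction of any distortion from comparing different patients at the two times be derived.

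**What to change.** Amend the Statistical analysis plan as follows.

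1. Extend the existing linear regression to quality of life, with frailty and the covariates already listed. Use the same frailty definition as the primary analysis, and name the instrument.
2. Report the adjusted frail versus non-frail difference with its 95% CI.
3. Choose the main contrast in advance and give the reason: either the 12-month score adjusted for the preoperative score, or the within-patient change. Report the other as a sensitivity analysis, and say that the two answer different questions in a non-randomised cohort and can disagree.
4. In patients with both forms, report preoperative means, 12-month means and within-patient change by frailty group. Apply the 10-point rule to within-patient change.
5. State that the result applies to survivors who return the 12-month form.

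The cost is a short wording change and a little more analysis. Both questionnaires are already scheduled at both times, so no new visits or forms are needed. The downside is a result limited to survivors who reply, with a precision that the documents do not allow anyone to state in advance.
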